**SPECIFIC OUTCOMES AND HYPOTHESIS:**

The primary outcome of this study is to compare core body temperature four hours after induction in patients having lower spinal surgery, of at least three hours in duration and using either a heated ventilator circuit (treatment group) or a standard ventilator circuit with a HME (control group). For any patient surgery with a core temperature not reaching four hours post-induction, the final esophageal temperature will be used. We hypothesize that the treatment group will have higher statistically significant temperatures four hours after induction or using the last recorded esophageal temperature for surgeries not reaching that timeframe compared to the control group.

A secondary outcome will compare overall patient temperature trends between the two groups, perioperatively. We hypothesize that the treatment group will have higher statistically significant temperatures perioperatively 60 minutes post-induction compared to the control group. An additional secondary outcome will compare patient shivering between the two groups. We hypothesize that the treatment group will have less shivering compared to the control group.

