22°C, but may be adjusted beyond this range at the surgeon's discretion and/or subject's condition. The room temperature will be documented for all subsequent subjects every hour using an in-room digital display temperature device. It is important to standardize flow settings and tidal volumes as both may impact the amount of delivered heat to the patient, and it is recognized that these settings may be difficult to maintain during induction or patient positioning as higher volumes are generally given. The ventilator flow setting will be maintained at  $\leq 2$ L/min or adjusted to meet the patient's needs during anesthetic maintenance, with tidal volumes 6-8ml/kg following patient positioning and induction. Patient randomization will assist with reducing any other potential sources of variation that may occur, such as patient exposure time during positioning.

**FIGURE 1:** Describes patient selection process

Patient's temperature will be measured and recorded in the preoperative area at least once prior to entering the OR suite. Intraoperative, patient's temperature will be measured and recorded within ten minutes or the first stable temperature reading after induction to establish a baseline. To allow for patient repositioning, the next temperature will be recorded within 30 minutes of the baseline esophageal temperature and every 10 minutes thereafter for the first hour post-induction, followed subsequently every 30 minutes until the patient is repositioned supine. Following the surgery, the patient will be transferred to the PACU, where the temperature will be measured and recorded at least once within 15 minutes of arrival (Figure 2). Oral temperatures (or axillary temperatures if an oral temperature cannot be obtained) will be used in the preoperative area, PACU, and ICU while esophageal temperatures will be measured in the OR suite after induction.

[figure not shown]
Patients will be monitored in the PACU for shivering as this can be an indicator of hypothermia. Any patients transferred directly to ICU from surgery will have a temperature recorded within 15 minutes of arrival. Any patient transferred to ICU will not be monitored for shivering. All patients' electronic medical records will be monitored through their hospital discharge, up to 30 days post-surgery to record any postoperative complications.

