## **STATISTICAL CONSIDERATIONS/ANALYSIS**

Based on previous studies, we anticipate the standard deviation of patient temperature is 0.6°C. Several studies have demonstrated that a 0.5°C temperature change is clinically relevant,

as patients have less intraoperative blood loss, fewer transfusions, decreased post-anesthesia recovery, and less shivering. Using the assumption that a standard deviation of patient temperature is 0.6°C and assuming that a difference between groups of 0.5°C is clinically relevant, we have determined that a total sample size of N=64 (N=32 per group) will provide a statistical power (two-tailed, alpha=0.05) of 90% to detect a clinically relevant difference between groups. In order to account for potential attrition due to cancelled surgery, inability to place an esophageal stethoscope with a temperature sensor, and/or unexpected surgery length <3 hours, we propose a total sample size of N=70 (N=35 per group). Group randomization will be performed using a randomization schedule prepared by the Division of Clinical Statistics with subjects randomized in blocks of 4. This will ensure that after every 4th patient is enrolled, there are an equal number assigned to each treatment arm. Using this randomization schedule, individuals who will not have any subject contact for the present study will prepare randomization envelopes, which will be labeled according to subject ID number and contain an index card indicating the intervention assignment (control group or treatment group) for the given subject. For enrolled and consented patients on the day of surgery in the AM admit areas (Alfred-1 or EPACU), a subject will be assigned the next sequential subject ID number and the appropriate sealed envelope will be opened to reveal the subject's randomized intervention assignment. This will occur before the patient is transferred to the OR suite.

Data will be summarized using mean±SD (or median 25th, 75th) for continuous variables and frequency percentages for nominal variables. For the primary analysis, the esophageal temperature four hours post-induction or using the last recorded esophageal temperature for surgeries not reaching that timeframe will be compared between the control group and treatment group using analysis of covariance (ANCOVA) with pre-induction temperature included as a

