covariate. This will account for any variation in pre-induction temperature, and the potential correlation between pre-induction temperature and the primary outcome temperature. In addition, a repeated measures analysis will be performed using all intraoperative esophageal temperatures recorded until surgery end-time, which will be defined as the last recorded esophageal temperature (for all patients). This analysis will be performed using mixed linear models with temperature as the dependent variable, time as a within subject effect, and treatment group as a between subject effect. Additional secondary outcomes will include shivering and temperature at PACU arrival. The frequency of any shivering during the PACU will each be compared between treatment groups using the chi-square test (or Fisher's exact test). Temperature at PACU arrival will be compared between groups using analysis of covariance (ANCOVA) as previously described. In all cases p-value  $\leq 0.05$  will be considered statistically significant.

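### The repeated-measures model omits the pre-induction temperature that the plan adjusts for in its two other temperature analyses, giving up precision and leaving chance baseline imbalance in a comparison of temperature levels

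*Combined protocol and SAP*

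**What the plan says.** The section STATISTICAL CONSIDERATIONS/ANALYSIS describes three analyses of temperature.

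- **Primary (four-hour or last esophageal reading).** An "analysis of covariance (ANCOVA) with pre-induction temperature included as a" covariate. The reason is given: "This will account for any variation in pre-induction temperature, and the potential correlation between pre-induction temperature and the primary outcome temperature".
- **PACU arrival.** "Temperature at PACU arrival will be compared between groups using analysis of covariance (ANCOVA) as previously described", so the same covariate carries over by reference.
- **Intraoperative series.** Between these two, "a repeated measures analysis will be performed using all intraoperative esophageal temperatures recorded until surgery end-time", fitted by "mixed linear models with temperature as the dependent variable, time as a within subject effect, and treatment group as a between subject effect". No covariate is listed, there is no link back to the primary model, and no other section adds one.

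Under SPECIFIC OUTCOMES AND HYPOTHESIS, the secondary outcome is the temperature trend, and the hypothesis is that the "treatment group will have higher statistically significant temperatures perioperatively 60 minutes post-induction compared to the control group". That is a statement about levels.

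Under MATERIALS AND METHODS, oral (or, failing that, axillary) readings "will be used in the preoperative area, PACU, and ICU while esophageal temperatures will be measured in the OR suite after induction". The preoperative reading is therefore the only temperature taken before induction, and it is not part of the mixed model's response series. Every patient should have one: it is to be recorded before entry to the operating suite, and eligibility requires it to lie between 36 and 38°C.

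**The concern.** The plan accepts that starting temperature may predict later temperature and adjusts for it in two of three temperature analyses. The third uses esophageal readings from the same patients, and its series contains the primary endpoint reading, yet the listed terms leave the covariate out.

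Two things are at stake for the trend comparison:

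- Between-patient variation that starting temperature could explain stays in the error, so the group difference is estimated less precisely than the data allow.
- If one arm happens to start warmer, part of that difference appears in the estimated group effect. The primary ANCOVA would remove it.

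**Working it through.** **Inputs from the plan:** SD 0.6°C; target difference 0.5°C; two-sided alpha 0.05; power 90%; 32 per arm (all from STATISTICAL CONSIDERATIONS/ANALYSIS). **Assumed:** rho, the correlation between pre-induction temperature and an intraoperative reading. The documents give no value, so 0 to 0.7 is shown.

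**1. The plan's own figure.** By the normal approximation, n per arm = 2 × (1.960 + 1.282)² × 0.6² / 0.5² = 30.3, rounded up to 31. With the noncentral t distribution, power is 0.898 at 31 per arm and 0.907 at 32. So 32 per arm (N=64) reproduces, and it takes no credit for a covariate.

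**2. Unadjusted standard error of a group difference at one time point.** 0.6 × sqrt(2/32) = 0.6 × 0.25 = 0.150°C.

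**3. Gain from adjustment.** Adjusted SE = 0.150 × sqrt(1 − rho²). Excess variance without adjustment = 1/(1 − rho²) − 1.

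**4. Carry-over of chance imbalance.** One standard error of the between-group baseline difference is sqrt(2/32) = 0.25 of a patient-level SD of the covariate. An imbalance of k such standard errors shifts the unadjusted estimate by k × rho × 0.150°C, whatever the covariate's SD.

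| rho | Adjusted SE (°C) | SE reduction | Excess variance if unadjusted | Shift, k = 1 (°C) | Shift, k = 2 (°C) |
|---|---|---|---|---|---|
| 0 | 0.150 | 0% | 0% | 0 | 0 |
| 0.2 | 0.147 | 2% | 4% | 0.03 | 0.06 |
| 0.3 | 0.143 | 5% | 10% | 0.045 | 0.09 |
| 0.5 | 0.130 | 13% | 33% | 0.075 | 0.15 |
| 0.7 | 0.107 | 29% | 96% | 0.105 | 0.21 |

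Estimating the extra coefficient multiplies the adjusted SE by about sqrt(1 + 1/60) = 1.008. At rho 0 adjustment therefore costs about 1%, and the other reductions are up to about 1 percentage point smaller. An imbalance of two standard errors or more, in either direction, is expected in about 5% of trials.

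**5. Check on the time-averaged effect.** A simulation assumed 32 per arm, 11 readings per patient, and compound symmetry with a within-patient correlation of 0.7. At rho 0.3, 0.5 and 0.7 the unadjusted group effect correlated with the baseline imbalance at 0.35, 0.59 and 0.82. After adjustment the correlation was about 0. The SD of the estimate fell by 6%, 19% and 42%. These falls exceed those in the table because averaging removes reading-to-reading noise, so the baseline explains a larger share of what remains.

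**The case against.** The strongest reply is that this is only a refinement to a secondary analysis, of unknown and possibly small benefit. Much of that stands.

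**Validity.** A reader might infer that the unadjusted model is biased or inflates type I error. It does neither: allocation is randomised 1:1. The loss is in precision, and the imbalance is a matter of chance.

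**Group-by-time contrasts.** A reader might also infer that the omission matters equally whichever contrast is tested. It does not. The first esophageal reading, which the plan calls a baseline, is one of the model's responses. A group-by-time contrast against it would cancel stable differences in starting level and remove much of the imbalance. An additive covariate would then change little. But no such term or contrast is stated, and the hypothesis concerns higher levels from 60 minutes, where the point holds. That first reading may also follow the start of heated gas: the controller is on before the circuit is connected, and the reading comes after intubation.

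**Size.** Rho could be low. The covariate is oral or axillary while the outcome is esophageal, and eligibility confines the covariate to 36–38°C. The Background describes a fall of 1–1.5°C in the first hour. The rule that switches forced air off and on around 36°C may further weaken dependence on starting temperature. The upper rows of the table should not be read as expected values.

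**Scale of imbalance.** The shifts are for one or two standard errors of the between-group difference. A gap of a full patient-level SD would shift the estimate by rho × 0.6°C (0.18°C at rho 0.3), but it equals four standard errors and is not a realistic chance outcome.

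**Agreement with the primary.** A reader might infer that adjustment would make the trend and primary results interchangeable. It would not: one uses the four-hour or last value, the other the whole series. Adjustment removes only one avoidable source of disagreement.

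**Conclusion.** The omission is clear on the text, and the plan's own rationale covers the analysis that lacks the covariate. For a comparison of levels, the unadjusted model is valid but less efficient than it could be, and it is exposed to chance imbalance. At 32 per arm and SD 0.6°C the SE gain at a single time runs from nothing (about a 1% loss) at rho 0 to 29% at rho 0.7. An imbalance of one standard error moves the estimate by 0.03 to 0.105°C over rho 0.2 to 0.7, which is 6% to 21% of the 0.5°C target.

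The omission itself is certain. Its size is not, because it rests on an assumed rho that may well be low, and on the group effect being tested as a level and not as change from the first esophageal reading. The primary ANCOVA and N=64 are untouched. This is an inexpensive improvement to a secondary analysis, not a flaw that invalidates it.

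**What to change.** In STATISTICAL CONSIDERATIONS/ANALYSIS, after the sentence that lists the mixed model's terms, add for example: *The model will include as a fixed effect the same pre-induction (preoperative-area) temperature used in the primary ANCOVA, together with its interaction with time.* The interaction lets the influence of starting temperature fade during surgery.

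Use the preoperative reading as the covariate, not the first esophageal reading, which may already follow the start of heated gas. Table 1 describes the primary outcome relative to the initial esophageal baseline while the ANCOVA uses pre-induction temperature, so the text should say which reading serves as baseline in each model. It would also help to name the group contrast to be tested, since the effect of the covariate depends on it.

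**Cost.** The covariate takes one sentence and no new data. It uses one parameter. The covariate-by-time term adds one more if time is linear, or about ten if time is categorical, since the recording schedule gives roughly 11 readings by four hours. Settle this before any comparison by group, so that whether to adjust is not decided after seeing results.

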Shivering in the PACU will be assessed at least every 30 minutes for a maximum of two hours using the Bedside Shivering Assessment Scale (BSAS) described by Badjatia et al (Table 1). This is a 4-point scale and rates shivering as the following: absent, mild, moderate, or severe (Table 2). Absent means "no shivering noted on palpation of the masseter, neck, or chest wall."67(p3243) Mild means "shivering localized to the neck and/or thorax only."67(p3243) Moderate means "shivering involves gross movement of the upper extremities (in addition to

neck and thorax),”(p3243) and severe means “shivering involves gross movements of the trunk and upper and lower extremities.”67(p3243) The BSAS demonstrated reliability among multiple users and was tested for validity using indirect calorimetry (IDC) at rest. IDC is often performed at rest and provides reliable, precise measurements of resting energy expenditure, which contribute largely to the total daily energy expenditure. Nurses in the PACU will be educated to use this scale by a team member associated with this study.

FIGURE 2: Describes perioperative timeline and outcome measurement events

11

**TABLE 1:** Describes study outcomes

OUTCOME	LOCATION	DESCRIPTION
Primary: Post-induction temperature	Intraoperative	Patient core temperature four hours post-induction or using the last recorded esophageal temperature for surgeries not reaching that timeframe compared to initial baseline esophageal temperature
Secondary Perioperative temperature	Intraoperative, postoperative	Patient temperature trends intraoperative to postoperative.
Shivering	Postoperative	Presence of shivering among patients in the PACU as described by Bajjatia et al.  Assessed every 30 minutes for a maximum of two hours.

**TABLE 2:** Describes Bedside Shivering Assessment Scale developed by Bajjatia et al.

Score	Definition
0	None: no shivering noted on palpation of the masseter, neck, or chest wall
1	Mild: shivering localized to the neck and/or thorax only
2	Moderate: shivering involves gross movement of the upper extremities (in addition to the neck and thorax)
3	Severe: shivering involves gross movements of the trunk and upper and lower extremities

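### As written, the arrival-temperature ANCOVA covers PACU arrivals only, although a comparable arrival reading is taken in patients sent directly to ICU and no planned analysis uses it

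*Combined protocol and SAP*

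**What the plan says.** The Statistical Considerations/Analysis section names the outcome and then its analysis, both times by reference to the PACU alone: "Additional secondary outcomes will include shivering and temperature at PACU arrival" and "Temperature at PACU arrival will be compared between groups using analysis of covariance (ANCOVA) as previously described".

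Materials and Methods sets out what is collected. For the PACU, it describes it as the place "where the temperature will be measured and recorded at least once within 15 minutes of arrival". For the other destination: "Any patients transferred directly to ICU from surgery will have a temperature recorded within 15 minutes of arrival". One rule on route covers both: "Oral temperatures (or axillary temperatures if an oral temperature cannot be obtained) will be used in the preoperative area, PACU, and ICU".

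The only outcome expressly withheld in ICU patients is shivering: "Any patient transferred to ICU will not be monitored for shivering". Table 1 describes the secondary temperature outcome as "Patient temperature trends intraoperative to postoperative", with no restriction to the PACU. The other secondary temperature analysis stops before the patient leaves the operating room: "a repeated measures analysis will be performed using all intraoperative esophageal temperatures recorded until surgery end-time".

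**The concern.** Set side by side, the two sections leave a reading with no use. The ICU-arrival temperature is collected on the same terms as the PACU one, yet the ANCOVA is worded for PACU arrivals and the mixed model takes only esophageal readings. An analyst who follows the text would leave ICU patients out of the arrival comparison, or would have to decide about them after seeing the data.

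The envelope is opened before the patient goes to the operating room, so destination after surgery is settled after randomisation. Restricting the analysis to one destination means that the arms compared are no longer exactly the arms randomised. Two things are at stake. Precision is lost in proportion to the number of ICU patients. Bias can also arise if transfer is related to both temperature and arm. The Background links hypothermia to blood loss, cardiac events and later extubation, and says that the trial takes longer operations and less healthy adults. A relation between temperature and ICU transfer is therefore plausible, but it is an inference and the plan does not state it.

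**Working it through.** **Inputs from the documents (Statistical Considerations/Analysis).** SD 0.6°C; difference 0.5°C; two-sided alpha 0.05; power 90%; 32 per group, raised to 35 per group for attrition. The SD and difference are stated for the sample size of the trial. The documents give no SD for the oral or axillary arrival reading, so both are borrowed here.

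**Assumptions.** ICU transfer of 10% to 20% (the documents give no rate). An unadjusted two-sample t-test stands in for the ANCOVA, because the correlation with the covariate is not given.

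**1. Reproduce the plan's figure.** The normal approximation is n per arm = 2 × (1.96 + 1.2816)² × (0.6/0.5)² = 2 × 10.51 × 1.44 = 30.3, rounded up to 31. The t-test version gives 31.25, rounded up to 32, which is the plan's 64 in total. Power at 32 per arm is 90.7%. The plan's figure reproduces.

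**2. Precision.** If a share f of each arm goes to ICU, n per arm becomes 35 × (1 − f) and the standard error grows by the factor 1/√(1 − f). Power comes from the noncentral t with noncentrality (0.5/0.6) × √(n/2).

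| ICU share f | n per arm | Increase in standard error | Noncentrality | Power |
|---|---|---|---|---|
| 0 | 35 | none | 3.49 | 93.0% |
| 10% | 31.5 | 5.4% | 3.31 | 90.2% |
| 20% | 28 | 11.8% | 3.12 | 86.5% |

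Starting instead from 32 per arm, with the whole attrition allowance used up, power is 90.7% with all patients, 87.4% at 10% and 83.2% at 20%.

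**3. Bias.** Suppose that ICU patients are c °C colder than PACU patients in the same arm. The arm mean equals the PACU mean minus f × c, so the PACU mean lies f × c above the arm mean. The PACU-only difference (treatment minus control) is therefore shifted by c × (f in treatment − f in control).

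- c = 0.5, treatment 10%, control 20%: 0.5 × (0.10 − 0.20) = −0.05°C.
- c = 0.5, 10% in both arms: 0.5 × 0 = 0.
- c = 0.8, treatment 10%, control 30% (a deliberately severe case): 0.8 × (0.10 − 0.30) = −0.16°C.

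The hypothesis is that treated patients are warmer, so a negative shift understates the benefit: more of the cold patients have been removed from the control arm. If more treated than control patients went to ICU, the sign would reverse.

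**4. Scale.** A shift of 0.05°C is one tenth of the 0.5°C target (0.05/0.5). It is about one third of the standard error with all patients included: 0.6 × √(2/35) = 0.143°C, and 0.05/0.143 = 0.35.

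**The case against.** The strongest reply is that the exclusion is inferred. Nowhere does the plan say that ICU patients are left out of the arrival ANCOVA. Where the authors wanted to withhold ICU patients they said so, and that was for shivering only. Requiring a timed ICU reading, and describing the outcome in Table 1 as running into the postoperative period, suggests that PACU arrival may be shorthand for arrival after surgery. A PACU-specific outcome also has a possible basis: the Background cites a quality measure for normothermia soon after PACU arrival. This stands, so a reader should not infer that a subgroup is knowingly discarded for no reason. The documents support only that ICU readings are omitted as the analysis is worded and that no reason is given. If it is shorthand, the wording still needs correcting.

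A reader might also infer that the attrition allowance is deficient because ICU transfer is not on its list. That does not follow. The allowance serves the primary outcome, an intraoperative esophageal temperature, and patients sent to ICU still contribute to it. The arrival outcome was not separately powered.

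The figures rest on assumptions. The power loss needs an assumed ICU rate and a borrowed SD and difference. The bias needs an ICU rate, a temperature gap and an imbalance between arms all at once. Transfer could instead reflect comorbidity or planned disposition. That also stands, and it is why the size is given as a range that includes zero bias.

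Finally, a reader might extend the point to shivering. That is a different outcome, and its ICU restriction is openly stated, so it is no part of this point.

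**Conclusion.** The point holds in a limited form. Followed as written, the plan compares arrival temperature in PACU arrivals only, makes no use of a comparable ICU reading that it collects, and so conditions one secondary comparison on an event after randomisation. Under the assumptions above, the cost in power is about 3 percentage points at 10% ICU transfer (93.0 − 90.2 = 2.8) and about 6.5 at 20% (93.0 − 86.5). Bias is zero if ICU shares and coldness are equal in both arms, and about 0.05°C against the treatment in the illustrative unequal case.

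The documents do not show that bias will occur or that transfer differs by arm. The primary analysis and the intraoperative repeated-measures analysis are untouched, and the effect on the trial's conclusions is probably modest. The change is still worth making, because the data will already be in hand and settling the rule beforehand removes a choice that could otherwise be made after the results are seen.

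**What to change.** - Define the secondary outcome as temperature within 15 minutes of arrival in PACU or ICU.
- Fit the planned ANCOVA to all randomised patients with an arrival reading, in the arm assigned.
- Report destination (PACU or ICU) and measurement route (oral or axillary) by arm.
- Keep the PACU-only ANCOVA as a sensitivity analysis.

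Route is better reported than used to select patients. An analysis confined to oral readings would condition on another feature that arises after randomisation.

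The cost is a sentence or two in the Statistical Considerations/Analysis section, a matching line in Table 1 and a few lines of analysis. It needs no extra patients or temperature measurements and no change in care; the route used for each reading must be noted if it is not already. The small downside is that ICU readings may more often be axillary, so the pooled outcome may be slightly noisier. Reporting route by arm makes that visible.
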